# 5.3b. Informed Consent Procedures for VA employee stakeholders (Aim 2b)

We are requesting a waiver of documentation of informed consent for this portion of the study as it does not exceed minimal risk. Participants will be provided with an Information Sheet describing the same aspects of the study as an informed consent form would do. It will be explained that the recordings will only be heard/viewed by authorized members of the research team and will be de-identified. Participants can stop the interview at any time. A copy of the VA CIRB information sheet will be provided to each stakeholder ahead of data collection. Stakeholders will have multiple opportunities to ask questions prior to data collection.

#### 5.4 Inclusion/Exclusion Criteria

#### 5.4a. Inclusion/Exclusion Criteria for Veterans (Aims 1 and 2a)

Several evaluation components will be used to assess eligibility. In keeping with the pragmatic nature of our design, we will have minimal exclusion criteria.

Participants eligible to receive an introductory letter will be those have received a qualifying pain diagnoses on at least 2 occasions, at least 90 days part, within the same pain category, during the previous 2 years. The pain categories were initially defined by Goulet et al using International Classification of Diseases, Ninth or Tenth Revision, Clinical Modification diagnostic codes (ICD-9-CM/ICD-10-CM) and updated based on our team's participation in the PMC3 Phenotypes and Outcomes Working Group. Participants must have received care at one of the study sites.

Screener questions will be asked (online via Qualtrics FedRAMP or over the phone) to assess whether the following are true:

- Eligible participants must have pain duration of ≥ 6 months, and moderate to severe pain intensity (defined as a numeric rating score of ≥ 4 on a 0 to 10 scale).
- Participants must have access to a smart phone that meets the requirements of the mobile app software (this is pragmatic as access to such devices would be required for participation in a non-research context).
- Participants must have access to a device (e.g., smart phone, iPad, desktop computer) that enables them to participate in online UMN Zoom meetings).
- Participants must be willing and able to download the mobile app onto their phone and agree to the app-required permission settings.
- Participants must have adequate wireless or cellular internet access on a daily basis in a private space (e.g., at home).
- Participants must be willing to meet via Zoom at the specific date and time that Mobile+Group sessions are held.
- Participants must be willing to attend all sessions of the arm to which they are randomized.

As part of the screener, participants will be asked whether they prefer to receive communication by phone, email, and/or text message. They will have the opportunity to provide their phone number to allow phone calls, email if they would like us to contact them by email using Qualtrics FedRAMP or the LAMP study email address ([contact]), and they can choose to provide their mobile phone number if they would like us to contact them via text message.

Study staff will conduct a medical chart review in the electronic medical record of all participants who meet the screening criteria, in order to exclude any patients with active psychotic symptoms, suicidality, severe depression, and/or active manic episode or poorly controlled bipolar disorder. Some experts consider these disorders as contraindications for MBIs.

We will not exclude Veterans who are prescribed medication or receiving other treatments for chronic pain. However, we will collect information about medication and other treatment use and take this into account in our analyses.

Besides meeting all eligibility criteria, PCT participants must also complete the baseline survey before randomization will occur.

# 5.4b. Inclusion/Exclusion Criteria for VA Employee Stakeholders (Aim 2b)

Participants will be VA employees who could provide input to guide the future implementation of LAMP (such as providers involved in treating pain). We will identify these participants with input from our facility, VISN, and national partners.

### 5.5 Study Evaluations

#### 5.5a. Study Evaluations for Veterans (Aims 1 and 2a)

**Data Collection.** Data will be collected using Qualtrics FedRAMP surveys, paper surveys, telephone surveys, the mobile application, and EHRs. These measures are described below and in Table 2.

Qualtrics FedRAMP electronic survey software accessed via the VA cloud will be used. Qualtrics FedRAMP has been approved for use from the VA OIT Security standpoint (Authority to Operate or ATO). The ATO status is currently approved for 1 year and a full 3-year ATO is in the works. (See ORD IT Service Catalog 190530 memo for more details.) Qualtrics FedRAMP surveys will contain a study ID number, time of data entry and limited individually identifiable information. Within the VA firewall, the study team at the VA will create a custom-built tracking app that will track each participant's enrollment and study status. Data will be routinely extracted from Qualtrics FedRAMP in the VA cloud and stored on secure CCDOR servers, using SQL database connections. All data will be stored and utilized within secure CCDOR servers that are part of the Minneapolis VAMC network and which operate behind the VA firewall. All data is tracked using a SQL database, with a GUI-front end system that restricts access to only those with approval to study data.

Qualtrics FedRAMP surveys will contain minimal individually identifying information. The only identifying information will be information that is self-reported by the participants (e.g. name, phone, email, which is best method of contact). No sensitive data will be stored outside of the VA protected environment. Once data are transferred for data analysis, data will be maintained on password-protected VA computers in the VA environment and on secure VA servers.

Study staff will monitor the functioning of the Qualtrics FedRAMP application. Only staff affiliated with this research protocol will have access to Qualtrics FedRAMP data collected for this study. The PI or her designee will be responsible for monitoring data storage location and transfer of data between the VA cloud and VA server.

We will have dedicated research personnel at the central Minneapolis site to coordinate study data acquisition based on regularly updated reports. We will use several strategies to follow-up with participants who have not completed their assessments. To help decrease the number of participants who don't complete their assessments, we will mail a newsletter between each survey and a reminder postcard shortly before each survey is emailed. After sending assessments, we will contact non-responders via their specified preferred method and using additional contact information they provided. We will encourage online completion but mail paper copies or complete surveys by phone as preferred. We will email, mail, call, and text participants with reminders to complete the surveys. The emails will be sent using the LAMP study email address or via Qualtrics FedRAMP. Text messages will be sent via Qualtrics FedRAMP. Participants will be contacted to follow-up on any missing data that doesn't seem deliberate (e.g., if a couple of survey pages are completely blank but the rest of the survey is answered, it is likely the couple pages got stuck together rather than deliberately skipped). Participant flow data using the Consolidated Standards of Reporting Trials (CONSORT) framework will be collected, including recruitment, enrollment, intervention adherence, intervention fidelity, and data collection rates.

For intervention participants, all mobile app data collected will occur via a secure cloud-based application designed by MEI Research Ltd to support data capture for research studies and will be accessed as part of the mobile application. Because we are collecting mobile app data, we will be temporarily storing IP addresses, URLs, device identifiers, serial numbers, since this type of mobile app data may need to be collected as participants use their smartphones to interact online with the study application. The secure cloud-based application designed by MEI Research Ltd. to support data capture for this research study must be accessed as part of the study intervention. As the participant's smart phone engages online with the study application some information (IP addresses, URLs, device identifiers, serial numbers) may be captured by the cloud-based application in order appropriately deliver the correct content to the participant's device. However, we will not use this information in our research or transfer it to the VA. Co-I [name] has successfully conducted VA-funded studies using this data collection approach.

**Data coordination and management.** Data collection and management will be overseen at the Minneapolis VA HSR&D Center of Innovation (COIN) by [name]. Regular meetings of investigators and study staff within and between sites will take place to routinely review data collection and management issues. To prevent improper use of any data collected for research projects conducted at the Minneapolis COIN we will use a combination of local Minneapolis VA secure servers as well as the national secure VA Informatics and Computing Infrastructure (VINCI) and the secure Qualtrics FedRAMP system in the VA cloud. The local VA secure servers facilitate data collection and provide a platform for the customized research tracking application, while the VINCI platform provides a robust environment for pooling the primary research collected data with direct connections to daily or weekly updated mirrors of nearly the entire VHA EHR. VINCI also provides access to extensive storage area networks, drives, file shares, databases, SharePoint for collaboration and correspondence sites, SAS/Grid, and servers containing virtual machines with an extensive collection of software called the VINCI Workspace. We will request access to the Joint Legacy Viewer (JLV) in order to capture the

highest follow-up response rate that is feasible. It is very important that we reach the participants in a timely manner; being able to access current address and phone numbers will help in tracking hard to reach participants. A secure link between local VA secure servers, the data collected on the MEI designed mobile applications, and Qualtrics FedRAMP will be created. Limited study specific data will be collected on the mobile applications and Qualtrics FedRAMP and will contain a study specific participant ID code. Only after the data are securely transferred to the local VA server environment will the mobile study data be linked to participant VHA data using the study ID. VINCI allows individual researchers and their staff the means to securely conduct their research projects within a secure and well controlled technical environment. All of these VA systems undergo backups of the servers nightly and servers are updated when new security patches become available. All individuals with administrative privileges to the VHA servers have been screened and have been assigned security clearance putting them in trusted positions to work with patient-level data.

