## 5.2 Recruitment Methods and Participant Enrollment

#### Aim 1

We anticipate recruiting up to 950 participants from our 4 sites, using our proactive recruitment protocol (see below). The subject population for our study will be chronic pain patients from the Minneapolis, Durham, Indianapolis, and Los Angeles VA medical centers They will be 18 years or older. Using this protocol, we plan to recruit up to 950 participants with about 40% being female. Participants will be randomized to one of the 3 study arms and asked to participate in the subsequent intervention. Thus 250 participants will be in each arm (Mobile+Group, Mobile, and UC). All participants will be asked to complete the screener, and then complete the baseline and 10-week, 6-month, and 12-month follow-up surveys. Participants will be given \$25 for each survey they complete (possible total of \$100). Completion of the eligibility components will result in randomization to one of the three study arms, (Mobile+Group MBI, Mobile MBI, or UC (1:1:1)).

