**Our Primary Outcome will be pain severity and functioning**, defined as a change in the Brief Pain Inventory (BPI) total score (assessed by survey). The Brief Pain Inventory (BPI) assesses two key domains—intensity and interference—recommended for pain studies and has been validated in primary care. The BPI is the average of pain intensity and pain interference scores. The pain intensity score is an average of 4 ratings of 0 (no pain) to 10 (pain as bad as you can imagine) for current, least, worst, and average pain in the past week. The pain interference score averages seven ratings, 0 (does not interfere) to 10 (interferes completely), of interference with general activity, mood, walking ability, normal work, relations with other people, sleep, and enjoyment of life. The BPI has been shown to be highly responsive to change in clinical trials and to have strong internal consistency (Cronbach's  $\alpha = 0.77$ ).

**Secondary Outcomes.** To facilitate data sharing and comparison between studies we have incorporated Common Data Elements (CDEs), for use in our patient surveys. Specifically, we will use measures from the PROMIS-29 Profile v2.0 Instrument (www.nihpromis.org) as recommended by the NIH Research Task Force. This includes quality of life, emotional functioning and mental health-related outcomes (anxiety, depression), and outcomes related to fatigue and sleep. Self-reported data will also be collected on PTSD symptoms using the PTSD checklist (PCL), version C, DSM-V update, and patient satisfaction (using a short measure used by investigators [name] and [name]). These outcomes will be assessed via survey.

Adverse events will be monitored throughout the study period, using a process similar to other MBIs with Veterans. Specifically, Veterans will be given contact information encouraged to report exacerbation of symptoms or adverse effects to the class facilitators or study coordinator.

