#### Expected participation in Phase 2 trial

We base proposed estimates on our experience conducting previous successful trials with Veterans with chronic pain (ACTION, SPACE, EPOCH, ECLIPSE). Study participants will be recruited from the Minneapolis, Indianapolis, Greater Los Angeles and Durham VA Health Care Systems, using a process successfully used in prior studies by members of our research team, and piloted during Phase 1 of this project. The four facilities have about 80,000 patients who meet our initial eligibility criteria. We estimate from our Phase 1 pilot a randomization rate of 2.5% but an increased randomization rate when using approach #2, email recruitment. Therefore, we will need to screen approximately 100,000 patients in order to reach our recruitment goal of up to 950 randomized. We want an approximately balanced sample of men and women. We estimate women will respond at up to 3 times the rate of men (approximately 4.5% for women and almost 2% for men). If we screen a large portion of the sample of eligible women (about 20,000) and about 1/3 of the eligible men (about 80,000), then we should reach our recruitment goal of up to 950 randomized, with nearly balanced men and women. Among those randomized, we are conservatively planning that up to 20% might be missing complete follow-up data but based on past work we believe the actual level of missing data will be closer

to 10-15%. Ultimately, this would yield a randomized N= up to 950 and with retention of 600 or greater participants at 6 and 12 months.

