  enrolled into the study they will be given a unique study ID number. This study ID number
  will be used as the unique identifier for the app. Participant self-reported data and app
  usage data that are collected via the app will only be identifiable using this study ID. All
  crosswalk files that link the study ID to other participant identifiable data will be kept securely
  within the VA firewall. App data will be securely transmitted from the secure MEI Research
  cloud servers to the VINCI platform.
- All typed field notes, electronic recordings, interview transcripts, and analytic notes will be stored on VA servers. During the data gathering process in the field, all entries will be made onto VA-sanctioned devices.

LAMP Version 16, March 25, 2024 VA Central IRB Protocol Template - version 10/26/2012 Page 49 of 60

- VHA CCDOR servers will be used for running the customized tracking application software that contains participant contact information. EHR data will be extracted from within the VHA's secure VINCI platform. Only once the app data are within the VA firewall will the app data be linked to the participant EHR data. Therefore, participant identifiable data will be robustly protected throughout the project lifecycle within the VA firewall.
- Reminders to complete surveys will be sent to the participant's preferred method of contact, phone, email, mail, or text. Continued non-response will activate reminders sent via other methods, including phone, email, mail, and text message. Email will be sent using the LAMP study email or via Qualtrics FedRAMP. Text messages will be sent via Qualtrics FedRAMP.
- ORD Guidelines regarding using email and text messaging for communicating with VA research participants, as drafted in the following document, will be followed: https://www.research.va.gov/resources/policies/guidance/draft-electronic-mailtext.pdf. This includes:
  - No PHI or PII will be transmitted by study personnel through unencrypted email or text message.
  - The following text will be included in all emails and text messages so as to try and prevent participants from including PHI or PII in their responses: "Email and texting is not secure. Please do not reply back to this message with any personal information or personal health information. Please call [contact]."

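### The plan describes no BPI-only fallback for survey non-responders; offering one at the last reminder is a cheap way that could reduce missing primary outcome data

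*Combined protocol and SAP*

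**What the plan says.** Section 5.5a (Data Collection) plans newsletters, postcards before each survey, and contact with non-responders by several routes: "We will email, mail, call, and text participants with reminders to complete the surveys". Other modes are offered for the same instrument: "We will encourage online completion but mail paper copies or complete surveys by phone as preferred". Section 7.0 escalates by route: "Continued non-response will activate reminders sent via other methods, including phone, email, mail, and text message". Section 5.5a also plans a records look-up for current addresses and phone numbers. The one item-level step concerns gaps that look accidental: "Participants will be contacted to follow-up on any missing data that doesn't seem deliberate". Section 5.2 pays $25 "for each survey they complete".

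The primary outcome is short. In 5.5a (Measures), "The BPI is the average of pain intensity and pain interference scores"; the intensity score "is an average of 4 ratings of 0 (no pain) to 10", and the interference score averages seven ratings. Table 2 lists many other survey measures at the same visits.

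On missing data, section 5.6 (Expected participation) says "we are conservatively planning that up to 20% might be missing complete follow-up data" and expects 10–15%. The General Analytic Approach reports completion above 90% per time point in earlier studies. It uses all available follow-up data in a mixed model for repeated measures, followed by weighted selection models as sensitivity analyses.

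**The concern.** Someone who will not sit through a long battery might still give 11 pain ratings. The plan never asks for that smaller contribution, although the reminders, the survey platform and the paper and phone routes are already in place. Because the re-contact rule covers apparently accidental gaps, a person who deliberately stops partway falls outside it. The item order is not given, so nothing ensures that the BPI is reached before a break-off.

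What is at stake is mostly bias. Participants know their arm (section 6.0), and section 2.0 reports low adherence and high attrition in published MBSR studies, up to 50% in some. Non-response could therefore depend on arm and on engagement with the programme. The selection models in 5.6 vary assumptions about unseen values. A short form could turn some of those values into observed ones.

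**Working it through.** **1. Is a fallback described anywhere?** Sections 5.2, 5.5a, 5.6 and 7.0 refer throughout to the surveys or assessments. The mode of contact and completion varies; the content does not. No shortened or primary-outcome-only form appears.

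**2. Item count.**

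| Instrument | Items | Source |
|---|---|---|
| BPI | 4 + 7 = 11 | 5.5a, Measures |
| PROMIS-29 | 29 | assumed from the instrument's name; the text refers only to measures taken from it |
| AMPS | 15 | 5.5a, Process Measures |
| PSEQ | 8 | 5.5a, Process Measures |
| Adverse-event checklist | 8 | 5.1, Risk vs. Potential Benefit |

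Sum: 11 + 29 + 15 + 8 + 8 = 71, and 11/71 = 15.5%. The PTSD checklist, catastrophizing, perceived stress, patient-rated improvement, treatment use and practice measures come on top without stated counts, so 71 is a fair floor.

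**3. The plan's own power figure.** Inputs from 5.6: 200 analysed per arm, standardised difference 0.33, alpha 0.05/3 = 0.0167 (taken as two-sided). Noncentrality = 0.33 × √(200/2) = 3.30. Two-sample noncentral-t power is 0.815, and the normal approximation gives 0.818. The stated 80% reproduces. So does the inflation for loss: 250 × 0.80 = 200.

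**4. Power if some missing participants are recovered.** With N randomised per arm, missing fraction m and recovered share r (assumed), analysed n = N(1 − m) + N·m·r. For N = 250, by the noncentral t:

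| m | r | n per arm | Still missing | Power at 0.33 SD |
|---|---|---|---|---|
| 20% | 0% | 200 | 20% | 81.5% |
| 20% | 10% | 205 | 18% | 82.5% |
| 20% | 25% | 212.5 | 15% | 84.1% |
| 20% | 50% | 225 | 10% | 86.3% |
| 10% | 0% | 225 | 10% | 86.3% |
| 10% | 25% | 231.25 | 7.5% | 87.4% |
| 10% | 50% | 237.5 | 5% | 88.3% |

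At the ceiling of 950 (about 316 per arm) with 20% missing, about 253 per arm remain and power is already about 90% with no recovery.

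This calculation treats a missing participant as contributing nothing. In the planned mixed model, someone who misses one visit still contributes the others, so the gains are approximate.

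**5. Exposure to response bias, in a deliberately severe case.** Suppose MBI-arm non-responders had no benefit and were missing at every visit, while usual-care missingness was uninformative. If responders benefit by d, the all-randomised effect is d(1 − m). After a share r is recovered, and if those recovered resemble those still missing, the observed effect is d(1 − m)/(1 − m + m·r). The overstatement is therefore 1/(1 − m(1 − r)).

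- m = 20%, r = 0: 1/0.80 = 1.25
- m = 20%, r = 25%: 1/0.85 = 1.18
- m = 20%, r = 50%: 1/0.90 = 1.11
- m = 10%, r = 0: 1/0.90 = 1.11

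**The case against.** The retention plan is already thorough, and the absence of one more tactic is neither an error nor an inconsistency. That stands, and it sets the weight of this point.

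A reader might infer that anyone who leaves part of the survey blank is lost for the primary outcome. The documents do not support this. Section 5.1 lets participants refuse any question, 5.5a expects partly blank returns, and 5.6 analyses all available data; nothing discards an answered BPI. The gap concerns people who return nothing or who stop before the BPI.

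A reader might also take the 20% as the share with no primary outcome data. Section 5.6 describes it as missing complete follow-up data, calls it conservative and expects less. With three follow-up visits, many of these people would still supply some BPI scores.

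Nor do the documents show that a short form would recover data. They do not separate refusal of a long survey from withdrawal or lost contact, and a shorter form does not help with people who cannot be reached. Recovery could be zero. It is also an inference from silence that staff would never take a few key ratings by phone: the plan neither describes nor forbids it.

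Finally, equal payment for 11 items could reward waiting, and anyone diverted to the short form loses the adverse-event checklist as well as the secondary outcomes at that visit. This cost is real, but small if the form goes only to people still silent at the last contact.

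What survives is narrower: the plan describes no short form, and sensitivity models cannot replace observed scores.

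**Conclusion.** The point holds as a low-cost improvement of minor weight. The plan's sample size calculation stands, and planned power does not fail without the change. At 250 per arm and 20% missing, the gain in power at 0.33 SD runs from nil to about 5 percentage points for assumed recovery of 0% to 50%. It is about 2 points at 10% missing with half recovered, and smaller again if more than 250 per arm are randomised.

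The better reason to act is exposure to response bias. In the severe case worked above, overstatement would fall from 1.25 to about 1.18 with a quarter recovered, or 1.11 with half. These factors illustrate a worst case and are not estimates: they rest on zero benefit among MBI non-responders, absence at all visits, uninformative missingness in usual care, and recovered people resembling those still missing.

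The item share rests on the 29 inferred from the PROMIS name. It changes little if a few of those items are not used.

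**What to change.** Amend section 5.5a as follows:

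1. Place the BPI first in each follow-up survey.
2. At the final reminder for the 10-week, 6-month and 12-month surveys, offer an 11-item BPI-only form by link, paper or phone, at the same day count and with the same payment in all three arms.
3. Flag these records. State in 5.6 that the primary mixed model includes them and that a sensitivity analysis leaves them out.
4. Report by arm how many BPI scores came from the short form.

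The cost is one short electronic and paper form and a protocol amendment; the contacts are already planned. The downside is that a few late responders might give only the BPI, losing their secondary outcomes and adverse-event checklist at that visit. The protocol is at Version 16 (March 2024), so the change helps only follow-up surveys that have not yet closed.
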